10.1.3 Covariates and Subgroups

All analyses of efficacy endpoints will be adjusted for the effect of the stratification factor of prior/current treatment with migraine prophylactic medication (current migraine prophylactic medication treatment vs prior migraine prophylactic medication treatment only vs no prior or current migraine prophylactic medication treatment) and the baseline value. The primary, secondary efficacy, and selected safety endpoints will be analyzed in the subgroups defined by the stratification factor as well as **baseline monthly migraine days (< 8 days vs ≥ 8 days), prior prophylactic failure status (failed any vs not failed any), and BMI (< median vs ≥ median).**

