3.2 Sample Size

The primary endpoint is the change from baseline in mean monthly migraine days over the last three months (months 4, 5, and 6) of the DBTP. Using the treatment effect compared to placebo of -1.12 and -1.30 for the AMG 334 70 mg and 140 mg dose groups, respectively and a common standard deviation of 2.8 based on a placebo-controlled dose-finding study of JNS019 (topiramate) in migraine patients (www.clinicaltrials.gov), the planned sample size of 131 subjects in the placebo, 70 mg and 140 mg dose groups will provide 90% and 96% power for a two-sided test with significance level of 0.05 to show the difference of AMG 334 70 mg and 140 mg compared to placebo, respectively. The proposed number of subjects in the 28 mg (n=66) dose group with the placebo (n=131), the 70 mg (n=131) and the 140 mg (n=131) dose groups is sufficient to demonstrate a dose-response using Multiple Comparison Procedure – Modelling (MCP-Mod) analysis with minimum power of 95% and provide estimates of response in a Japanese population, using an assumed treatment effect of -0.55 for the AMG 334 28 mg dose group.

Power calculations are derived through nQuery 7.0.

4. Study Endpoints and Covariates

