10.5.1 Analyses of Primary and Secondary Efficacy Endpoints

For the primary analyses at the end of DBTP, the continuous primary and secondary endpoints will be tested using a linear mixed model based on observed monthly data from 24-week DBTP with appropriate contrasts provided in [Appendix B](#) for pairwise comparisons for the corresponding efficacy endpoints: change from baseline in mean monthly values.

The model will include treatment, visit, treatment by visit interaction, stratification variable and baseline value as covariates. If applicable, the first-order autoregressive covariance structure is assumed. Least squares means (LSMs) for each treatment group, standard errors, associated 95% confidence intervals, difference of LSMs compared to placebo group, associated 95% confidence intervals and nominal two-sided p-values will be tabulated by visit and treatment, as well as for the mean monthly values over the last 3 months in DBTP.

For binary endpoints, adjusted odds ratios compared to placebo group, associated 95% confidence intervals and nominal two-sided p-values will be tabulated by visit and treatment.

Sensitivity analysis described below will be performed for the primary and secondary endpoints:

1. Summary statistics and ANCOVA model for continuous endpoints (logistic regression model for binary endpoints) by visit using imputed data by LOCF (NRI for binary endpoint). Factor of treatment, baseline covariate and stratification variable will be included in the model.
2. Inverse probability weighted generalized estimation equation (IPW GEE) model on the primary and secondary endpoints.
3. MI with assumption of MAR
4. Primary summary and analysis method based on per protocol analysis set.
5. Primary summary and analysis by the subgroup of
 - Prior/current treatment with migraine prophylactic medication (current migraine prophylactic medication treatment vs prior migraine prophylactic medication treatment only vs no prior or current migraine prophylactic medication treatment)
 - BMI (< median vs. \geq median)
 - Baseline monthly migraine days (< 8 vs \geq 8)
 - Treatment failure of prior migraine prophylactic medications
6. Primary summary and analysis method with interaction: If the inclusion criterion at the 0.15 level is met, the interaction of treatment group by stratification variable will be included in the model as sensitivity analysis for the primary analysis method.

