The purpose of the subgroup analyses is to explore if the treatment effect varies across subgroups of interest. Subgroup analyses are performed for primary and secondary efficacy endpoints using the same method as Primary Summary and Analysis Method but performed within each described subgroup.

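### SAP 10.5.1 sets out to explore whether the treatment effect varies across subgroups, but plans no between-subgroup contrast for BMI, baseline migraine days or prior prophylactic failure

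*SAP*

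**What the plan says.** SAP 10.5.1 states the aim: "The purpose of the subgroup analyses is to explore if the treatment effect varies across subgroups of interest". The next sentence carries over the primary method for the primary and secondary endpoints, "but performed within each described subgroup". In the same section, that method yields least squares mean differences from placebo with 95% confidence intervals and nominal two-sided p-values, by visit and for the months 4-6 mean.

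SAP 7.8 and item 5 of the sensitivity list in SAP 10.5.1 name four factors: the three-level stratification factor, BMI split at the median, baseline monthly migraine days (<8 vs ≥8), and failure of prior prophylactic medication. Protocol 10.1.3 says that endpoints "will be analyzed in the subgroups defined by the stratification factor as well as" the same other three factors, and adds no test of heterogeneity.

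One interaction is planned. Under item 6 of that list, if a criterion at the 0.15 level is met, "the interaction of treatment group by stratification variable will be included in the model as sensitivity analysis". It covers the stratification factor only. Neither document says how a difference between subgroup levels should be read.

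**The concern.** Whether an effect differs between two groups of subjects is answered by the difference between the two effects and its uncertainty. A test of drug against placebo inside each group answers another question. Each subgroup holds only part of the sample, so power is lower, and one level can fall below 0.05 while the other does not, even when the true effects are equal.

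For three of the four factors, the planned tables would set such p-values side by side with nothing that compares them. A reader could then take a pattern that chance produces often as a sign that the drug works only above the median BMI, say, or only in subjects with more migraine days. At stake is the reading of the subgroup tables, not the trial's main result.

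**Working it through.** **Inputs (SAP 3.2).** "Using the treatment effect compared to placebo of -1.12 and -1.30 for the AMG 334 70 mg and 140 mg dose groups"; "a common standard deviation of 2.8"; 131 subjects per arm for placebo, 70 mg and 140 mg; two-sided 0.05.

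**Assumptions not in the documents.** Every factor splits 50:50 (given only for BMI, by the median), the factors are independent of one another, and the true effect is the same at every level. Tests are two-sample t tests without covariate adjustment.

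**The plan's own figure.** The SAP says that "the planned sample size of 131 subjects in the placebo, 70 mg and 140 mg dose groups will provide 90% and 96% power". A two-sample t calculation with n = 131 per arm gives 89.7% for 1.12 and 96.3% for 1.30, so the figure reproduces.

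**Power inside one half.** With n = 65.5 per arm, the standard error is 2.8 × √(2/65.5) = 0.489 days. Power p is 62% (70 mg) and 75% (140 mg).

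**Exactly one half significant, same true effect.** The halves contain different subjects, so the chance is 2p(1 − p):
- 70 mg: 2 × 0.6225 × 0.3775 = 0.47
- 140 mg: 2 × 0.7509 × 0.2491 = 0.37

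**Three factors and two doses together.** The same subjects are split three ways and both doses share the placebo arm, so these chances cannot simply be multiplied. I simulated 8,000 trials per scenario. The Phase 3 effects follow from Protocol 2.3: 3.23 − 1.83 = 1.40 and 3.67 − 1.83 = 1.84.

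| Result under a common true effect | Planning effects 1.12 / 1.30 | Phase 3 effects 1.40 / 1.84 |
|---|---|---|
| One factor, exactly one level significant (70 / 140 mg) | 47% / 38% | 32% / 8% |
| At least one of three factors (70 / 140 mg) | 72% / 60% | 52% / 16% |
| At least one of three factors, either dose | 85% | 56% |
| False interaction, per test at 0.05 | 5% | 5% |
| Any false interaction among the same six tests | 25% | 25% |

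Six independent tests would give 1 − 0.95^6 = 26.5%, close to the simulated 25%.

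**Sensitivity.** Uneven splits raise the figures: with the other two factors at 40:60 and 30:70, the either-dose figure is about 90%, and at 30:70 and 20:80 about 94%. A smaller SD lowers them: at SD 2.4 the chance for one even factor is 36% (70 mg) and 22% (140 mg), and at SD 2.0 it is 19% and 8%. Baseline adjustment would act in that direction.

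**Precision of the direct contrast.** For an even split, the standard error of the difference between the two effects is 2.8 × √(4/65.5) = 0.69 days. Power at 0.05 is Φ(1.12/0.69 − 1.96) = 37% for a difference of 1.12 days, and 82% for a difference of 2 days.

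**The case against.** The strongest reply is that these analyses are exploratory and that the tables hold more than p-values. The SAP uses the word explore, calls the p-values nominal and lists the subgroups among the sensitivity analyses. Estimates and 95% confidence intervals are reported at each level. The levels contain different subjects, so a careful reader can subtract one estimate from the other and obtain an approximate interval. This stands. A reader might infer that the planned tables cannot answer the SAP's question, but the contrast is left unreported rather than made unobtainable.

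Four other inferences are also unsupported:
- **That the SAP plans no interaction at all.** Item 6 plans one for the stratification factor. It is conditional, it is a sensitivity analysis, and it covers one factor of four.
- **That any single subgroup will usually mislead.** For one evenly split factor the chance is 37-47%, below one half. Only the pooled set passes one half, and with the Phase 3 effects only modestly.
- **That the fix takes the error from 85% to 5%.** The first figure is for six comparisons and the second for one test. The like-for-like comparison is about 85% with about 25%.
- **That the dose conclusions are at risk.** Those rest on the fixed-sequence test (Protocol 10.4.3, SAP 5) and on the dose-response modelling in Protocol 10.5.2. No passage uses subgroup results for dose choice.

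It is also fair to say that the SAP sets no rule of reading significance against non-significance. Equally, it sets no other rule, and its tables supply the p-values that invite that reading.

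**Conclusion.** The point holds in a limited form. For BMI, baseline migraine days and prior prophylactic failure, the stated purpose and the method do not match: no between-subgroup estimate or test is planned. For the stratification factor there is only a conditional interaction, and the SAP does not say whether the result of the 0.15-level check will be reported.

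Under the planning values and a common true effect, chance alone gives a significant-in-one-level-only pattern in 47% (70 mg) and 37% (140 mg) of trials for one even two-level factor. Over the three factors and two doses the figure is about 85%, or about 56% with the Phase 3 effects, against about 25% for any false interaction. The pooled figures rest on the assumed 50:50 splits, independence between factors and unadjusted tests. The primary conclusion and its type I error are not affected. The change is worth making because it is cheap and matches the analysis to its stated aim.

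**What to change.** Amend the subgroup text in SAP 10.5.1 as follows:
- **Continuous endpoints.** For each subgroup factor, fit one model on the Efficacy Analysis Set: the primary model plus subgroup, subgroup-by-visit, treatment-by-subgroup and treatment-by-subgroup-by-visit terms. Report the between-subgroup difference in the months 4-6 treatment effect, per dose, with its 95% CI and an exploratory interaction p-value.
- **50% responder endpoint.** Report a test of homogeneity of the odds ratio across subgroup levels, or add a treatment-by-subgroup term to the logistic model already planned as a sensitivity analysis.
- **Presentation.** Keep the within-subgroup estimates and 95% CIs. State that differences between subgroups will be judged on the interaction contrast, not on which within-subgroup p-values fall below 0.05.

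The cost is SAP wording and a little more programming. The interaction test has low power (about 37% for a 1.12-day difference with an even split). The estimate and its interval should therefore lead, and the text should say that a non-significant interaction does not show that the effect is constant.

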10.5.2 Analyses of Exploratory Efficacy Endpoints

For exploratory efficacy endpoints as specified in [Section 9.3](#), summary statistics and primary analysis method will be conduct in the same way as that for the primary endpoint.

The exploratory efficacy endpoints at each assessment time will be analyzed using the repeated measures linear mixed effects model (a generalized linear mixed model for dichotomized variables) that includes treatment group, baseline values, stratification factor, scheduled visit, and the interaction of treatment and scheduled visit without any imputation for missing data. The least squares mean (or odds ratio) of treatment group and placebo with associated 95% confidence intervals and p-values will be reported.

10.5.3 Analyses of Efficacy Endpoints in Open-Label Treatment Phase

For the OLTP of the study, descriptive summaries of efficacy endpoints will be tabulated by randomized treatment group and visit based on observed data without imputation.

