1.3 Exploratory

- To evaluate the effect of AMG 334 compared to placebo on change from baseline in headache impact scores as measured by the Headache Impact Test (HIT-6)
- To evaluate the month of onset of action of AMG 334 compared to placebo as assessed by monthly migraine days
- To evaluate the effect of AMG 334 compared to placebo on the change from baseline in mean monthly migraine attacks
- To evaluate the effect of AMG 334 compared to placebo on change from baseline in mean monthly headache (migraine and non-migraine headache) days
- To evaluate the effect of AMG 334 compared to placebo on the proportion of subjects with at least 75% reduction from baseline in mean monthly migraine days
- To evaluate the effect of AMG 334 compared to placebo on the proportion of subjects with 100% reduction from baseline in mean monthly migraine days
- To evaluate the effect of AMG 334 compared to placebo on change from baseline in monthly acute headache medication treatment days
- To evaluate the effect of AMG 334 compared to placebo on change from baseline in monthly hours of migraine headache
- To evaluate the effect of AMG 334 compared to placebo on change from baseline in monthly average severity of migraine pain
- To evaluate the effect of AMG 334 compared to placebo on change from baseline in mean monthly migraine days with severe pain
- To evaluate the effect of AMG 334 compared to placebo on change from baseline in mean monthly hours of severe migraine pain
- To evaluate the effect of AMG 334 compared to placebo on migraine pain interference with daily activities as measured by the migraine symptom interference items

- To evaluate the effect of AMG 334 compared to placebo on the change from baseline in the overall impact on everyday activities score as measured by the Migraine Physical Function stand-alone item
- To evaluate AMG 334 pharmacokinetics (PK) in subjects with migraine and characterize the exposure-response (E-R) relationships for efficacy and safety endpoints
- To investigate the dose-response relationship of AMG 334 for efficacy
- CCI [REDACTED]
- CCI [REDACTED]
- To evaluate the long-term safety, tolerability and maintenance of effect of AMG 334 after 100 weeks of treatment

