7.2.24 Open-label Treatment Phase

The following procedures are to be completed during the **OLTP** at time points designated in the Schedule of Assessments ([Table 3](#)):

- Confirmation that the subject may enter the **OLTP**: The subject has completed the double-blind treatment phase and did not end double-blind investigational product early, continues to provide informed consent, and is appropriate for continued treatment. The investigator should consider the appropriateness for continued treatment, if the subject:
 - Developed any unstable or clinically significant medical condition, laboratory or ECG abnormality following randomization into the double-blind treatment phase that, in the opinion of the investigator, would pose a risk to subject safety or interfere with the study evaluation, procedures, or completion. Note: Any ECG abnormality noted by the central reader must be evaluated by the investigator and discussed with the Amgen medical monitor as deemed necessary to determine if the ECG finding is representative of an unstable or clinically significant medical condition.
 - Experienced a serious adverse event in the double-blind treatment phase and the investigator determined that there was a reasonable possibility that the event may have been caused by investigational medicinal product.
- Entry of the subject into the **OLTP** using the IVR/IWR System
- Registration of the subject's end of investigational product and/or end of study (as relevant) using the IVR/IWR System
- Body weight measurement
- Vital signs: systolic/diastolic blood pressure, heart rate, and body temperature
- Laboratory assessments using the central laboratory: urine drug screen (performed at the investigator's discretion based on clinical suspicion), chemistry and hematology panels
- Pregnancy testing (urine)
- ECG

- PK sampling (serum)
- Anti-AMG 334 antibody serum sampling
- The subject is to interact with the eDiary every day and bring his/her eDiary to every study visit, as noted in the Schedule of Assessments table. Please refer to [Section 7.2.13](#) and the eDiary manual for details.
- COAs, migraine symptom interference items, and the Migraine Physical Function Impact stand-alone item
- HIT-6. The subject will complete these PROs while in the clinic. For each study visit, these PROs should be completed prior to invasive procedures (eg, blood draws).
- C-SSRS
- **Employment status**
- Concomitant medications recording

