- Administration of open-label AMG 334 70 mg QM SC or **140 mg QM SC**. The first dose of open-label investigational product is to be administered only after completion of all week 24 procedures. In general, administration of investigational product should be the last procedure performed at each study visit.
- **After IRB approval of Protocol Amendment 2, the 24-week double-blind treatment phase is followed by a 76-week OLTP with dose determined by the subject's week 48 status:**
 - (1) **Subjects who have already completed the week 48 visit will continue to receive AMG 334 70 mg QM SC (OL70) for a total of 76 weeks, following the open label assessments in [Table 3](#).**
 - (2) **Subjects who have not yet completed the double-blind treatment phase and are not yet in the open-label phase will receive AMG 334 140 mg QM SC (OL140) upon entering the open-label phase and continue receiving open-label AMG 334 140 mg QM SC for 76 weeks.**
 - (3) **Subjects who have not yet completed the week 48 visit but are in the open-label phase receiving AMG 334 70 mg QM SC must increase their dose to AMG 334 140 mg QM SC and continue receiving open-label AMG 334 140 mg QM SC until the week 100 visit (OL70-140) for a total open-label phase duration of 76 weeks. The dose increase should be done at the first available opportunity, defined as the first visit after IRB approval of Protocol Amendment 2. Refer to [Table 3](#) for assessments to be collected at the visit of the dose increase and 12 weeks after the dose increase. At the time of the dose increase, the End of Open-Label 70 mg eCRF page will need to be completed as subjects will be transitioning from 70 mg to 140 mg.**
- Serious and non-serious adverse event collection/recording/reporting. (Note: Serious and non-serious adverse events are to be collected through 16 weeks after the last dose of investigational product)
- **Adverse device effects collection/recording/reporting**
- Product complaints recording

A subject who discontinues open-label investigational product or the study during the OLTP will complete the week 100/ET visit and the safety follow-up visit 16 weeks after the last dose of investigational product.

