10.4.4 Final Analysis

The objective of the final analysis is to evaluate the long-term profile of migraine days and adverse events of AMG 334 in subjects with migraine after the 24-week double-blind treatment phase, **OLTP**, and safety follow-up. The final analysis for the study, including all study periods and all data, will be performed at the end of the trial. In addition to the primary analysis, efficacy data and safety data from the **OLTP**, the safety follow-up will

be tabulated by double-blind treatment group as well as by aggregated overall AMG 334 treatment group; no formal testing will be conducted.

Final Analysis activities are commenced based on achieving the End of Trial milestone described in [Section 3.6.2](#).

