2.3 Exploratory

- To evaluate the effect of AMG 334 compared to placebo on change from baseline in headache impact scores as measured by the Headache Impact Test (HIT-6)
- To evaluate the month of onset of action of AMG 334 compared to placebo as assessed by monthly migraine days
- To evaluate the effect of AMG 334 compared to placebo on the change from baseline in mean monthly migraine attacks
- To evaluate the effect of AMG 334 compared to placebo on change from baseline in mean monthly headache (migraine and non-migraine headache) days

- To evaluate the effect of AMG 334 compared to placebo on the proportion of subjects with at least 75% reduction from baseline in mean monthly migraine days
- To evaluate the effect of AMG 334 compared to placebo on the proportion of subjects with 100% reduction from baseline in mean monthly migraine days
- To evaluate the effect of AMG 334 compared to placebo on change from baseline in monthly acute headache medication treatment days
- To evaluate the effect of AMG 334 compared to placebo on change from baseline in monthly hours of migraine headache
- To evaluate the effect of AMG 334 compared to placebo on change from baseline in monthly average severity of migraine pain
- To evaluate the effect of AMG 334 compared to placebo on change from baseline in mean monthly migraine days with severe pain
- To evaluate the effect of AMG 334 compared to placebo on change from baseline in mean monthly hours of severe migraine pain
- To evaluate the effect of AMG 334 compared to placebo on migraine pain interference with daily activities as measured by the migraine symptom interference items
- To evaluate the effect of AMG 334 compared to placebo on the change from baseline in the overall impact on everyday activities score as measured by the Migraine Physical Function stand-alone item
- To evaluate AMG 334 pharmacokinetics (PK) in subjects with migraine and characterize the exposure-response (E-R) relationships for efficacy and safety endpoints
- To investigate the dose-response relationship of AMG 334 for efficacy
- CCI [REDACTED]
- [REDACTED]
- [REDACTED]
- To evaluate the long-term safety, tolerability and maintenance of effect of AMG 334 after 76 weeks of treatment

3. Study Overview

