7.4 Open-Label Treatment Phase Set

The Open-Label Treatment Phase Set (OLTPS) will consist of all subjects receiving at least one dose of AMG 334 in the OLTP. This analysis set will be used when summarizing data collected during the OLTP.

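### Open-label efficacy is summarised on observed data only, so response-related dropout could make the responder rate hold or rise; a responder table over all open-label entrants is needed beside it

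*SAP*

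**What the plan says.** - **Objective.** Protocol 1.3 (exploratory): "To evaluate the long-term safety, tolerability and maintenance of effect of AMG 334 after 100 weeks of treatment". SAP 2.3 still has "maintenance of effect of AMG 334 after 76 weeks of treatment", because the SAP was written on Protocol 1.0, with a 52-week open-label phase (SAP 1 and 3.1).
- **Who is in the phase.** Protocol 7.2.24 lists as a condition of entry: "The subject has completed the double-blind treatment phase and did not end double-blind investigational product early". The SAP 7.4 analysis set "will consist of all subjects receiving at least one dose of AMG 334 in the OLTP".
- **After stopping.** Protocol 7.2.24: "A subject who discontinues open-label investigational product or the study during the OLTP will complete the week 100/ET visit", followed by the safety follow-up visit. No other efficacy visits are scheduled for such subjects. Under Protocol 7.2.13 the diary after Week 52 runs only in Weeks 72–76 and from Week 96 to the Week 100/ET visit.
- **Analysis.** SAP 10.5.3: "descriptive summaries of efficacy endpoints will be tabulated by randomized treatment group and visit based on observed data without imputation". Protocol 10.4.4 says the open-label and follow-up data will "be tabulated by double-blind treatment group as well as by aggregated overall AMG 334 treatment group; no formal testing will be conducted".
- **Missing data.** LOCF, non-responder imputation, inverse-probability-weighted GEE and multiple imputation are specified in SAP 9.3.3 and 10.5.1 for the double-blind phase only. In that phase the 50% responder analysis counts missing as non-response (Protocol 10.5.3, SAP 10.5).
- **Baselines.** SAP 10.1 plans change from both the study baseline and a pre-open-label baseline. SAP 6.3 defines only the first.

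**The concern.** Maintenance asks whether subjects who had a response keep it. A table of observed values by visit answers a different question: how those still providing diary data are doing at that visit. If subjects with poor control leave more often, the remaining group looks better at each later visit even when no individual has changed. A flat or improving responder curve to Week 100 would then be open to two readings, and no planned responder table would separate them.

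The objective is exploratory, the phase has no control group and nothing is tested, so no error rate is at stake. What is at stake is the wording that the final report can support.

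**Working it through.** **Figures in the documents.** They give no open-label dropout rate and no maintenance figure, so there is no stated result to reproduce on this point. The time frame is consistent within each version: 24 + 76 = 100 weeks in the Protocol and 24 + 52 = 76 in the SAP. A subject randomised to placebo has 100 − 24 = 76 weeks of AMG 334 at Week 100. The SD of 2.8 used below comes from Protocol 10.2. With 131 per arm and effects of 1.12 and 1.30 days it gives 89.9% and 96.4% power, agreeing with the stated 90% and 96%. The power is not in dispute.

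**1. Responder rate.** Assumptions: 100 entrants, 50 of them responders, and nobody's status changes. L subjects leave.
- Three non-responders leave per responder: observed rate = (50 − 0.25L)/(100 − L); rate over all entrants with leavers as non-responders = (50 − 0.25L)/100.
- Leaving unrelated to response: observed rate = (50 − 0.5L)/(100 − L); rate over all entrants = (50 − 0.5L)/100.

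| L | Observed, 3:1 | All entrants, 3:1 | Observed, unrelated | All entrants, unrelated |
|---|---|---|---|---|
| 10 | 47.5/90 = 52.8% | 47.5% | 50% | 45% |
| 20 | 45/80 = 56.3% | 45.0% | 50% | 40% |
| 30 | 42.5/70 = 60.7% | 42.5% | 50% | 35% |

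The last column shows the price of the fixed denominator: it falls even when leaving has nothing to do with efficacy.

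**2. Mean change from study baseline.** Each subject's change x is held constant: normal, mean −3.67 days (the 140 mg result in the global Phase 3 study, Protocol 2.3), SD 2.8. The chance of leaving is p(x) = 1/(1 + exp(−(a + b(x + 3.67)))), where b = ln(OR per day of poorer response) and a is set to give the stated loss. The observed mean is E[x(1 − p)]/E[1 − p]. The bound, where only the worst responders leave, is 2.8 × φ(z)/(1 − loss), with z the upper quantile at that loss. At 20% it is 2.8 × 0.280/0.80 = 0.98 days.

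| Loss | OR 1.0 | OR 1.25 | OR 1.5 | Apparent gain, days (OR 1.25 to 1.5) | Bound, days |
|---|---|---|---|---|---|
| 5% | −3.67 | −3.75 | −3.81 | 0.09 to 0.15 | 0.30 |
| 10% | −3.67 | −3.84 | −3.95 | 0.17 to 0.28 | 0.55 |
| 20% | −3.67 | −4.00 | −4.20 | 0.33 to 0.53 | 0.98 |
| 30% | −3.67 | −4.15 | −4.44 | 0.49 to 0.77 | 1.39 |

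For scale, the planned effects against placebo are 1.12 and 1.30 days.

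**3. Change from the pre-open-label baseline.** With every response constant, this change is 0 for each subject and so 0 at every visit, whatever the dropout. If no one improves it cannot show a gain. It can still recover: if 20 of 100 subjects worsen by 2 days and then leave, the mean goes from (20 × 2)/100 = +0.4 days to 0 at the next visit. It gives no information on the responder rate.

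**4. Entry rule and columns.** The entry rule acts once, before the first open-label visit. It makes entrants differ from the randomised population but cannot make Week 100 differ from Week 28; only later dropout can. SAP 10.5.3 and Protocol 10.4.4 both tabulate by randomised group, so former placebo subjects have their own column. The aggregated column is additional. If it includes them, they make up 131/459 = 28.5% of it at the planned allocation, before any dropout.

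**The case against.** The strongest reply is that SAP 10.1 already plans a within-subject comparison through the pre-open-label baseline. For the mean, this largely stands. A reader might infer that the plan has no means of telling a maintained effect from the loss of non-responders; the documents do not support that. What remains is that this baseline is not defined, that subjects who worsen and leave drop out of it, and that it does not touch the responder rate.

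Attrition will also be visible: SAP 10.2 tabulates open-label entry, discontinuation and reasons, and SAP 10.1 reports numbers of observations by visit. That shows how many left. It does not show the responder rate with them counted.

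Protocol 8.1 lets a subject stop product, stay in the study and agree to further data collection, so it would be too strong to say that everyone who stops gives no later data. Protocol 7.2.24 nevertheless schedules only the Week 100/ET visit and the safety follow-up.

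Finally, the SAP text was written for a phase ending at Week 76. The 76-week and 100-week objectives belong to different protocol versions and are not evidence of a faulty method. It is still the only open-label efficacy rule in the SAP, and it would carry over unless changed.

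**Conclusion.** The concern holds in limited form. As planned, the observed 50% responder rate and the mean change from study baseline can hold or rise through dropout alone. In the illustrations the responder rate rises by about 3 to 11 points for 10% to 30% loss, and the mean improves by about 0.1 to 0.8 days for 5% to 30% loss. These sizes rest on assumed dropout, an assumed link between leaving and response, an assumed 50% responder rate, and a mean and SD taken from other trials. With no such link the shift is zero. The documents show that the drift is possible, not that it will occur.

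Two stronger readings are not supported. The entry rule does not cause drift between open-label visits; it limits whom the results describe. Former placebo subjects are not hidden, since each randomised group is tabulated, and Protocol 10.4.4 does not say whether they are in the aggregated column. This is a worthwhile low-cost improvement to an exploratory, untested analysis.

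**What to change.** When the SAP is aligned with Amendment 2, keep the observed-data tables and make these changes in SAP 10.5.3 and Protocol 10.4.4:

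1. **Add a fixed-denominator responder table.** Give the 50% responder rate at Weeks 72–76 and 96–100 by randomised group, with all open-label entrants as denominator and missing counted as non-response, which is the double-blind rule. Show it beside the observed rate and the number observed over the number entered.
2. **Use the within-subject comparison already planned.** Define the pre-open-label baseline as the month 6 (Week 24) monthly value. Read the change as maintenance only in subjects randomised to AMG 334, by randomised group and open-label dose sequence. For former placebo subjects it measures the start of treatment. A pooled comparison of completers would mix these subjects and the dose changes, and would still omit those who left.
3. **Label the overall column.** Restrict any overall 100-week figure to subjects randomised to AMG 334, or label former placebo subjects as 76 weeks.
4. **State the population.** Describe the results as applying to open-label entrants.

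The cost is a small amount of descriptive output from data already collected, with no change to visits or procedures. The downside is that item 1 is conservative for subjects who leave for reasons unrelated to efficacy, which is why it belongs beside the observed rate and does not replace it.
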